8.2.4.2. By-Subject Overall Outcomes Subgroup Analysis

Overall success rates at EOT, TOC, and LFU visits will be analyzed in the micro-MITT population in subgroups similar to those described in Section 8.1.2.4.

8.2.4.3. By-Pathogen Overall Outcomes Analysis

In the micro-MITT population, provide the proportion of subjects in each treatment group with overall success by gram-negative pathogens on EOT, TOC, and LFU visit.

In addition to the above analyses in the micro-MITT, extended micro-MITT, CR-MITT, and ME populations, the overall success rate at EOT, TOC, and LFU visits for subjects in the corresponding treatment groups will be listed by the species of gram-negative pathogens detected at baseline, and by the MIC values at baseline for IMI-XNW4107 and IMI\REL.

8.3. Exploratory Endpoint

Healthcare utilization of subjects assessed at LFU visit as follows:

- Total number of days spent in hospital post-randomization in the MITT population.
- Total days spent in intensive care unit (ICU) post-randomization in the MITT population.
- Total days spent on mechanical ventilation post-randomization for the subgroup of subjects on mechanical ventilation at enrollment (VABP/ventilated HABP) in the MITT population.

The total number of days after the above randomization is calculated as follows:

- Data from hospitalization/ICU/mechanical ventilation where the date is missing and the status is not sustained will not be included in the calculations.

- The date of the LFU visit was used as the cutoff date for hospitalization/ICU/mechanical ventilation status that was continuous, and the study end date was used as the cutoff date for missing LFU visits.
- The cutoff for hospitalization/ICU/mechanical ventilation was after the LFU visit, with the LFU visit date used for the cutoff (for missing LFU visits, the study end date was used as the cutoff date).
- If time was not missing from the data collection, the total length of each hospital/ICU/mechanical ventilation stay after randomization was calculated in segments (if needed) (in hours) and then summed to calculate the total length of time, which was then converted to the total number of days (divided by 24).
- During the segmentation process, if the start and cut-off times were missing from the data collection, 12:00 of the day was used to fill them in.
- During segmentation, if only the start time is missing from the data collection, use 0:00 of the day to fill in.
- During the segmentation process, if only the cut-off time was missing from the data collection, it was filled in using 23:59 of the day.

Post-randomization periods = Cut-off time - Start time (the later of the filled random time and the corresponding occurrence time)

If there were multiple segments of hospitalization/ICU/mechanical ventilation for the same subject, the results for each segment were summed to calculate the total duration (in hours), which was then converted to the total number of days (divided by 24).

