1.1.3. Exploratory Objectives

Healthcare Utilization

- To determine healthcare utilization up to Day 28 post-randomization in the IMI-XNW4107 group compared to the IMI/REL group in the MITT population.

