3.5. Missing Data and Outliers

3.5.1. Missing Data

As a general rule, missing data are not filled in unless otherwise specified. The exceptions are listed below.

Section 9.1.5.2 describes how to handle missing or incomplete AE start dates. The treatment of prior and concomitant medications is described in Section 7.1. For missing primary estimate target analyses, the fill rules are described in Section 8.1.2. For missing microbiologic data, the fill rule is described in Section 3.6.2. For missing clinical outcomes, microbiologic outcomes, and overall assessment results, the rules for filling in are described in Sections 8.2.2.1, 8.2.3.1, and

8.2.4.1. Sections 8.3.1 and 5.2 describe the treatment of incomplete dates for exploratory endpoints. Details of the filling of these missing data can be found in the relevant sections of this document.

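### SAP 8.3 sums only the dated segments, so an ended hospital, ICU or ventilation stay with a missing date drops out of the subject's total

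*SAP*

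**What the plan says.** The SAP's exploratory objective (1.1.3) is "To determine healthcare utilization up to Day 28 post-randomization" in the two arms. Section 8.3 defines three totals: days in hospital, in the ICU and on mechanical ventilation. The last is restricted to subjects ventilated at enrollment.

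The derivation rules in 8.3 are:

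- **Ended stay, date missing:** data "where the date is missing and the status is not sustained will not be included in the calculations". The bullet does not say which date, start or end.
- **Ongoing stay:** kept and truncated. "The date of the LFU visit was used as the cutoff date for hospitalization/ICU/mechanical ventilation status that was continuous", with the study end date used if there was no LFU visit.
- **Date present, clock time missing:** kept and filled. For example, "if only the cut-off time was missing from the data collection, it was filled in using 23:59 of the day".
- **Length of a segment:** "Cut-off time - Start time (the later of the filled random time and the corresponding occurrence time", so only post-randomization time counts.
- **Several segments:** "the results for each segment were summed to calculate the total duration (in hours", and the sum is divided by 24.

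SAP 3.5.1 sets the default: "As a general rule, missing data are not filled in unless otherwise specified". It refers the reader to 8.3.1 and 5.2 for incomplete dates in the exploratory endpoints. Section 8.3.1 contains no such rule, and 5.2 fills clock times only for ICU status at baseline.

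**The concern.** Leaving one component out of a sum has the same arithmetic effect as giving it the value zero. The 3.5.1 default of not filling in missing data does not cover this, because the subject still receives a total and that total is known to be too low. Nothing in 8.3 or 8.3.1 flags the partial total, bounds it, sets it to missing or counts the subjects concerned.

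The section is also uneven. An ongoing stay is truncated and kept, and a stay without a clock time is filled and kept. Only an ended stay without a date disappears, even in cases where the missing date is not needed.

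At stake are the descriptive utilization means and the by-subject listing in 8.3.1. No hypothesis test uses these totals.

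**Working it through.** The plan states no figure for this rule, so there is none to reproduce. The check applies the 8.3 rule to hypothetical segments.

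**Inputs from the documents.** Study day 1 is the randomization date (SAP 3.7.1), so an LFU visit on Day 28 (SAP 1.2, window ±3 days) falls 27 days after randomization. Counted length = min(end, LFU) − max(randomization, start). Ended segments with a missing date are skipped, and the rest are added. All segment dates below are assumptions, in days from randomization.

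| Case | Recorded segments | True total | Total under 8.3 |
|---|---|---|---|
| A | −3 to 8; second starts at 12, end date missing (truly 20) | 8 + 8 = 16 | 8 |
| B | only segment starts at −3, end date missing (truly 14) | 14 | 0 if an empty sum is coded as 0, otherwise missing; not specified |
| C | only segment, start date missing, in that status at randomization, ends at 14 | 14 | as B, although 14 − 0 = 14 is known |
| D | first segment ended before randomization, end date missing; second −2 to 9 | 9 | 9 (no loss) |

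Case A loses the whole 8-day segment. Recorded dates bound its total: at least 8, and at most 8 + (27 − 12) = 23.

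Case C shows the rule discarding known time. It bears most directly on the ventilation total, whose population is by definition ventilated at enrollment (planned as at least 50% of subjects, SAP 1.2).

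Case D marks the limit of the problem: a segment that ended before randomization costs nothing.

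**Shift in a group mean when partial sums are reported.** Shift = share of subjects affected × mean days lost per affected subject. Both inputs are assumed:

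- 1% × 5 days = 0.05 day
- 5% × 10 days = 0.5 day
- 10% × 14 days = 1.4 days

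**Would setting the total to missing be better?** Assume 5% of subjects are affected, each losing 12 days, and unaffected subjects average 10 days. The true mean is 0.95 × 10 + 0.05 × (dated days + 12), and the 8.3 mean is 0.95 × 10 + 0.05 × dated days. With affected totals set to missing, the mean is 10.0.

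| Dated days in affected subjects | True mean | 8.3 rule | Set to missing |
|---|---|---|---|
| 3 | 10.25 | 9.65 | 10.0 |
| 10 | 10.6 | 10.0 | 10.0 |
| 14 | 10.8 | 10.2 | 10.0 |

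Setting to missing is better in the first row, equal in the second and worse in the third. When affected subjects have longer true stays than the others, removing them also lowers the mean.

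**The case against.** The strongest reply is that the bullet speaks of data, not segments, and never says that the subject keeps a partial total. It could be read as dropping the subject, and a subject with a single undated segment would then simply be missing under the 3.5.1 default. That reading is possible but less natural, because the bullet sits among the rules for building each subject's total and is followed by a rule for summing segments. What stands is that the single-segment case is unspecified. A reader might infer that every affected subject is recorded with zero days, and the text does not support that.

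The second reply is that few dates may be missing by database lock. Protocol Appendix 5 provides for source verification, data queries and automated checks for missing data, and SAP 2.3 delays the final analysis until open issues are resolved or confirmed unresolvable. This is fair. It limits the frequency but supplies no rule for the dates that remain unresolvable.

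Two stronger inferences are tempting. One is that long stays with transfers are the ones most likely to lack dates. The other is that the rule creates a spurious difference between arms. The documents say nothing about which stays lack dates or whether this differs by arm, and the trial is double-blind. Neither inference is supported.

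**Conclusion.** The point holds in a limited form. On the record-level reading, a subject with several segments is understated by the part of the dropped segment that falls after randomization and before the cutoff. A subject whose only segment is dropped has an undefined result. A segment already running at randomization is lost even when only its unneeded start date is missing.

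The assumed ranges put the shift in a group mean at 0.05 to 1.4 days. The true value depends on the frequency of missing dates, which the documents do not give. The endpoints are exploratory and summarized descriptively, and no primary, secondary or safety analysis is touched. The impact is probably small, and this is a minor improvement to the SAP.

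**What to change.** Replace the bullet in SAP 8.3 with three rules:

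1. If only the start date is missing and the subject was in that status at randomization, count the segment from randomization.
2. For any other undated ended segment that may extend past randomization, do not report the partial sum as the total. Bound the segment with recorded dates: start no earlier than randomization, and end no later than discharge, death or the LFU/study-end cutoff. Summarize the totals under the lower and the upper bound. This also settles the single-segment case.
3. Report the number of affected subjects by arm for each of the three resources.

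Setting the total to missing should not be the only remedy, for the reason shown in the second table of the working. The cross-reference in SAP 3.5.1 should point to 8.3, where the rules actually are.

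The cost is a few lines of SAP text, a little extra programming for three resources, and a range instead of a single value for a few subjects. No new data are needed.

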1.3. Sample Size and Test Efficacy

Assuming an all-cause mortality rate of 10% for both treatment groups, a 2:1 randomization ratio, and a one-sided significance level of 0.025, a trial of 450 subjects will have more than 90% power to show non-inferiority with a 10% non-inferiority margin.

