8.3.1. Exploratory Analysis

Descriptive statistics will be provided for the total number of days spent in the hospital/ in the ICU/ on mechanical ventilation from the time of post-randomization for the MITT population. Number of days on mechanical ventilation will be analyzed in the subgroup of ventilated subjects at baseline.

Provides a list of the total number of days in the hospital after randomization, the total number of days in the intensive care unit, and the total number of days on mechanical ventilation after randomization for the subjects, sorted in ascending order by subject number.

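### SAP 8.3 cuts hospital, ICU and ventilator days at the actual late follow-up date instead of Day 28 and has no rule for death: a cheap, low-priority repair to an exploratory summary

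*SAP*

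**What the plan says.** SAP 1.1.3 sets the horizon: "To determine healthcare utilization up to Day 28 post-randomization in the IMI-XNW4107 group compared to the IMI/REL group in the MITT population". It is a comparison of arms with a fixed end.

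SAP 8.3 and Protocol 2.2.5 tie the endpoint to the LFU visit. For stays still running, SAP 8.3 states: "The date of the LFU visit was used as the cutoff date for hospitalization/ICU/mechanical ventilation status that was continuous". A stay that ends after LFU is cut on the same date. If there is no LFU visit, both cases use the study end date, which 8.3 does not define.

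SAP 1.2 places LFU at Day 28 ±3. SAP 3.7.4 lets visits happen outside their window and analyses them under the nominal visit. SAP 3.7.1 numbers the randomization date as Day 1.

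The analysis in SAP 8.3.1 is a summary only: "Descriptive statistics will be provided for the total number of days spent in the hospital/ in the ICU/ on mechanical ventilation". It covers the MITT population, with ventilator days limited to subjects ventilated at baseline. Neither 8.3 nor 8.3.1 mentions death. Protocol 4.3.2 lists death among the reasons for leaving the study.

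**The concern.** There are two separate problems.

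The first is explicit. The objective ends at Day 28, but the counting rule ends on whatever date the LFU visit took place. Subjects are then counted over windows of different length, and none need match the stated one.

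The second follows from silence. A subject who dies before LFU has no LFU visit, so the count stops at or before death. In a mean of days over all MITT subjects, early death and early discharge look alike: both give a small number. The trial's primary endpoint is death, so a shorter mean stay in one arm could partly reflect more deaths there. At stake is how a descriptive table is read.

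**Working it through.** **Plan's own figure.** The plan gives no figure for healthcare use. Its sample-size statement concerns the primary endpoint: "a trial of 450 subjects will have more than 90% power to show non-inferiority with a 10% non-inferiority margin". With 300 and 150 subjects and 10% mortality in both arms, the standard error is √(0.10 × 0.90 × (1/300 + 1/150)) = 0.03. Power is Φ(0.10/0.03 − 1.96) = Φ(1.37) = 91.5%. The statement reproduces and does not depend on the day-count rule.

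**Window.** With Day 1 as randomization, Day d is d − 1 elapsed days:

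- LFU on Day 25: 24 days
- Day 28, the stated horizon: 27 days
- LFU on Day 31: 30 days

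The spread between two subjects with the same continuing stay is 30 − 24 = 6 days, or 6/27 = 22% of the horizon. It is larger if a visit is out of window. Only subjects still in hospital, in ICU or on a ventilator at LFU, or whose stay ends after it, are affected. If a share s of an arm is still in hospital at LFU, a one-day difference between arms in average LFU timing moves the arm mean by s days. For assumed s of 20% to 60%, that is 0.2 to 0.6 days.

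**Study end date.** For a subject with no LFU visit, the natural reading is that subject's own last date in the study. Protocol 3.3, however, defines end of study as the last subject's last visit. Read that way, a stay recorded as ongoing at death would run on past the death. The term needs a definition.

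**Death, direction.** If the course before death is unchanged, surviving longer can only add days or leave the count equal. Each extra death therefore lowers that arm's total or leaves it unchanged.

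**Death, size.** Let p be the proportion who die before the cutoff, S the survivors' mean days, and T the mean days counted in those who die (time to death, if they remain in hospital until then). The arm mean is (1 − p)S + pT. With the same S and T in both arms, the difference is (pA − pB)(T − S). For days alive and out of hospital through Day 28, with death scored 0, the arm mean is (1 − p)(27 − S) and the difference is −(pA − pB)(27 − S).

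The documents give none of these quantities. Assume pA = 20%, pB = 10% and T = 7:

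| S (days) | Difference in total days, 0.10 × (7 − S) | Difference in days alive and out, −0.10 × (27 − S) |
|---|---|---|
| 15 | −0.8 | −1.2 |
| 20 | −1.3 | −0.7 |
| 25 | −1.8 | −0.2 |

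The left column reads as a saving for the arm with more deaths. The right column shows the same arm doing worse. At 15% against 10%, every entry halves.

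**Where the direction fails.** The total-days difference favours the higher-mortality arm only when T < S. With S = 5 and T = 10, plausible for ventilator days, it is 0.10 × (10 − 5) = +0.5 days against that arm.

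**The case against.** The endpoint is exploratory, has no test or margin, and touches no primary, secondary or safety analysis. Mortality is reported directly: Day 14 as the primary endpoint and Day 28 as a secondary, with Kaplan-Meier curves and a Cox model. A large mortality gap would also show in the primary result. With true Day 14 rates of 20% and 10%, the chance of passing non-inferiority is about 2.5%; with 15% and 10%, about 35%. The reasons given in SAP section 14 describe mortality in the trial as low, which limits the gap between arms. If days have a standard deviation of 8.5 (an assumption), the standard error of the arm difference is 8.5 × √(1/300 + 1/150) = 0.85 days, so the artefact at a 5-point gap (0.4 to 0.9 days) is about one standard error or less. All of this stands, and it sets the priority.

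SAP 3.7.4 also says that data from a late visit should relate to the day the visit required, with Day 28 survival as its example. That general sentence does not repair 8.3, which specifically names the LFU visit date. At best the two conflict.

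The cutoff agrees with Protocol 2.2.5, which ties the endpoint to LFU. That explains the rule but does not reconcile it with the Day 28 objective.

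Days alive and free is a different estimand from total days, and death does end resource use. This also stands: it argues for adding a row and against replacing the endpoint.

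A reader might infer that the LFU window biases the comparison of arms. The documents do not support that. The window is the same for both blinded arms and nothing suggests different visit timing, so the expected effect is noise.

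**Conclusion.** The point holds in two parts of unequal certainty. The mismatch between a Day 28 objective and an LFU-date cutoff is explicit, and allows 24 to 30 elapsed days where 27 is meant. That the count ends at death is an inference from the missing rule, the study-end-date cutoff and death being a reason for withdrawal; the SAP does not say so in words. The inference is sound, and it means a raw MITT mean mixes shorter use with earlier death.

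The size of the death effect rests wholly on assumed mortality, stay and time to death: 0.8 to 1.8 days in the scenarios with a 10-point gap, and half that with 5 points. A reader might conclude that the arm with more deaths must look better on all three measures. It need not. That requires mean days to death to be below survivors' mean days, which may fail for ventilator days. A reader might also think the primary conclusion is weakened; it is not touched. This is a cheap improvement of low priority.

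**What to change.** In SAP 8.3:

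- Truncate hospital, ICU and ventilator days at Day 28 for everyone.
- Define the study end date as the subject's own last date in the study, or the date of death if the subject died.
- Flag and count, by arm, subjects whose follow-up ends before Day 28, including those with LFU on Days 25 to 27. Truncation cannot supply their missing days.
- Keep total days as the protocol endpoint. Add days alive and free of hospital, ICU and ventilator through Day 28, with death scored 0, as a supplementary descriptive row.
- Show raw days separately for survivors and deaths. This split is descriptive, because survival is itself an outcome.

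The cost is one more derived variable per measure, a few table rows and an entry in SAP section 11. The dates and survival status are already collected.

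### SAP 8.3 fills a lone missing start or stop time to the end of the day that lengthens the stay, but two missing times to midday, so affected hospital, ICU and ventilator segments gain about half a day on average and a shared day can be counted twice

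*SAP*

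**What the plan says.** SAP 8.3 defines three exploratory totals: days in hospital, days in ICU, and days on mechanical ventilation for subjects ventilated at enrollment. Each is built from segments measured in hours. Three rules cover missing clock times:

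- Both times missing: "if the start and cut-off times were missing from the data collection, 12:00 of the day was used to fill them in".
- Start only: "During segmentation, if only the start time is missing from the data collection, use 0:00 of the day to fill in".
- Stop only: "During the segmentation process, if only the cut-off time was missing from the data collection, it was filled in using 23:59 of the day".

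The word for exclusivity in the second and third rules shows that the first is the case where both are missing.

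Segment length is given as "Post-randomization periods = Cut-off time - Start time (the later of the filled random time and the corresponding occurrence time"), so a start before randomization is replaced by the randomization time. The segments of one subject are added and the sum is divided by 24. The section has no cap at elapsed time and no rule for two segments that share a date.

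SAP 8.3.1 gives the use: "Descriptive statistics will be provided for the total number of days spent in the hospital/ in the ICU/ on mechanical ventilation", with a by-subject listing. Protocol 8.6.3 likewise plans description only.

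**The concern.** The three rules do not follow one principle. A lone missing time is set where it makes the segment longest, while two missing times are set at the centre of the day. A record with one known time can therefore be further from the truth than a record with none. Stays of the same true length can get different totals according to which times a site wrote down. Because segments are simply added, a day on which one segment ends and the next begins can be counted twice.

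These totals are the whole of the trial's healthcare-utilization assessment (Protocol 2.2.5). At stake are their accuracy and the plausibility of the by-subject listing, where a total longer than the time elapsed would be visible.

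**Working it through.** **Inputs.** The fill rules, the segment formula and the summation come from SAP 8.3. The SAP states no numerical result for this rule, so there is no figure to reproduce. The documents give neither the distribution of clock times nor the frequency of missing ones; the distributions below are assumptions.

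**1. One stay, four patterns of missing times.** Randomization Day 1; true stay Day 3 12:00 to Day 8 12:00, which is 5 × 24 = 120 h.

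| Missing | Filled stay | Hours | Days |
|---|---|---|---|
| none | D3 12:00 – D8 12:00 | 120.00 | 5.00 |
| start only | D3 0:00 – D8 12:00 | 132.00 | 5.50 |
| stop only | D3 12:00 – D8 23:59 | 131.98 | 5.50 |
| both | D3 12:00 – D8 12:00 | 120.00 | 5.00 |

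**2. Mean error.** Let s and e be the true start and stop clock times in hours, for a multi-day segment that starts after the randomization day. The error is derived minus true length:

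- start only: s − 0 = s
- stop only: 23.98 − e
- both: (s − 12) + (12 − e) = s − e

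| Assumed clock times (uniform) | Start only | Stop only | Both |
|---|---|---|---|
| 0–24 h | +12.0 h | +12.0 h | 0.0 h |
| 8–20 h | +14.0 h | +10.0 h | 0.0 h |
| 8–18 h | +13.0 h | +11.0 h | 0.0 h |

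For a single record with one time missing, the error lies between 0 and just under 24 h. An average of 0.5 day is 0.5/2 = 25% of a 2-day segment, 0.5/5 = 10% of a 5-day segment and 0.5/10 = 5% of a 10-day segment.

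**3. Start before the randomization day.** True post-randomization length 122 h (randomized Day 3 10:00, stop Day 8 12:00). With only the start missing, the result is 122.00 h, an error of 0. With only the stop missing, it is 133.98 h, an error of +11.98 h.

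**4. Adjoining segments.** Ventilated from Day 2 08:00 to Day 5 (stop time missing), then from Day 5 (start time missing) to Day 8 10:00.

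- First segment: D2 08:00 to D5 23:59 = 3 d 15 h 59 min = 3.67 d.
- Second segment: D5 0:00 to D8 10:00 = 3 d 10 h = 3.42 d.
- Sum before rounding: 7.08 d. Elapsed from first start to last stop: 6 d 2 h = 6.08 d.

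The excess is 23 h 59 min: Day 5 is counted twice.

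**5. An admission time that should not matter.** Randomized Day 1 10:00 while already in hospital; discharged Day 11 at 12:00, with that time not recorded. The true length is 10 d 2 h = 10.08 d. If the earlier admission time was recorded, only the stop is missing and the result is 10 d 13 h 59 min = 10.58 d. If the admission time is missing too, and counts as the missing start, the stop becomes 12:00 and the result is 10.08 d.

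**6. Same-day segment.** True 09:00 to 15:00, 6 h. The rule gives 14.98 h with the stop missing, 15.00 h with the start missing, and 0 h with both missing.

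**The case against.** **It looks deliberate.** SAP 5.2 fills ICU admission with 00:00 and departure with 23:59, and counting a partly documented day in full is a recognisable resource-use convention. This does not rescue the rule. The 5.2 fill settles a yes/no question, whether the subject was in ICU at first dose, where wide bounds are harmless; 8.3 measures a duration. A consistent longest-stay convention would also use the extremes when both times are missing.

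**The error is not always upward.** A reader might infer that every filled time lengthens the stay. The segment formula rules this out, since a missing start before the randomization day adds nothing (step 3). The HABP and VABP definitions in Protocol 4.1 (onset at least 48 hours after hospitalization, or ventilation for at least 48 hours) mean that many first hospital and ventilator segments will have begun by then. This objection stands and confines start-fill inflation to later segments.

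**Midday is not unbiased everywhere.** A same-day segment with both times missing derives as 0 h (step 6). For a segment that began before randomization with both times missing, only the stop fill counts. If stops were uniform over 8–20 h, with mean 14, the error would average 12 − 14 = −2 h. This also stands.

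**Step 5 rests on one reading.** If start time means the later of randomization and admission, as in the segment formula, the start is known, only the stop is missing, and both versions give 10.58 d. The words about what is missing from the data collection allow either reading, so this is an ambiguity and not a contradiction.

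**The consequence is small.** The double count in step 4 needs two segments sharing a date with boundary times unrecorded, and nothing in the documents says how often that happens. No test or confidence interval is planned for these totals. A reader might infer a biased treatment comparison, but the documents give no reason to expect missing times to differ between blinded arms.

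**Conclusion.** The rule is internally inconsistent and, followed exactly, can produce a total longer than the time elapsed. Under uniform clock times, the average gain is about 0.5 day for a segment with only its stop missing, or with only its start missing and beginning after the randomization day. Under the daytime distributions tried, it is 10 to 14 h. A multi-day segment that starts after the randomization day with both times missing has no average error. Adjoining segments with stop and start times missing on the same date gain about one full day between them.

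The effect is confined to the exploratory, descriptive totals and does not touch the mortality analyses. It is equal in expectation across arms if missingness is balanced. The effect on a group mean cannot be computed, because the frequency of missing times is not given. This is a worthwhile clean-up of low priority.

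**What to change.** In SAP 8.3, replace the three missing-time rules with these:

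1. Replace a pre-randomization start by the randomization time before applying any missing-time rule. That time then counts as a recorded start, which removes the ambiguity in step 5.
2. Fill any missing start or stop time with 12:00 of that day.
3. Where the segment's other time is recorded on the same date, use the midpoint of the feasible interval instead, so that the stop never precedes the start.
4. Do not let a segment start before the previous segment of the same type ended.

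**Check.** The stay in step 1 becomes 5.00 d under every pattern. Step 4 becomes 3 d 4 h + 2 d 22 h = 6 d 2 h = 6.08 d, equal to the elapsed time. Step 5 gives 10.08 d whether or not the admission time was recorded. In step 6, a missing stop is set to the midpoint of 09:00 and 24:00, which is 16:30 (7.5 h), and a missing start to the midpoint of 0:00 and 15:00, which is 07:30 (7.5 h), against a true 6 h.

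**Cost.** A few lines of SAP text and slightly more programming than now; no new data. Rules 3 and 4 are needed because a plain 12:00 fill would give a negative length if, say, the recorded stop were 09:00 on the same day. A same-day segment with both times missing would still derive as 0 h. If the SAP is already final, SAP 1 provides for documenting the change in the clinical study report.
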